## Study Protocol

### I. Hypotheses and Specific Aims:

The primary objective of this randomized controlled trial is to determine efficacy of physical activity behavior-change telerehabilitation on improving physical activity after total knee arthroplasty (TKA).

**Aim 1:** To determine if PAB (Physical Activity Behavior-Change) intervention results in improved physical activity after TKA compared to the control group (CTL). Physical activity will be measured using accelerometer-based wearable sensors and self-reported daily activity (Life-Space Assessment).

**Hypothesis 1.1:** The PAB group will have greater increases in accelerometer-assessed daily step count (primary outcome) and percent time engaged in standing & walking activity than the CTL group from PREOP to POST2 (primary endpoint), and group differences will persist at POST3.

**Hypothesis 1.2:** The PAB group will have greater improvements in Life-Space Assessment scores than the CTL group from PREOP to POST2 (primary endpoint), and group differences will persist at POST3.

**Aim 2:** To determine if PAB intervention results in better physical function after TKA compared to the CTL group. Physical function will be measured with standardized performance-based (30-Second Chair-Stand Test, Timed Up-and-Go, Six-Minute Walk Test) and self-report (Western Ontario and McMaster Universities Osteoarthritis Index [WOMAC] and Veterans RAND 12-Item Health Survey [VR-12]) measures.

**Hypothesis 2:** The PAB group will have greater improvements in all functional outcomes compared to the CTL group at POST2 and POST3 test points, with outcomes meeting clinically meaningful thresholds.

**Exploratory Aim:** To identify predictors underlying responsiveness to PAB rehabilitation (i.e., change in average daily step count) from PREOP to POST2 in the PAB group.

**Hypothesis 3:** We expect preoperative daily step count and physical activity-related psychosocial factors (self-efficacy, stage of change, social support, fear of falling) will be significant determinants of intervention responsiveness, in addition to key demographic, anthropometric, and comorbidity determinants.

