## CONSORT Flow Diagram

[figure not shown]

Figure 3. Anticipated CONSORT Flow Diagram

Inclusion criteria: 50-85 years of age at enrollment, Veteran, and planned unilateral primary TKA.

Exclusion criteria: severe non-surgical limb pain (pain >5/10 on non-surgical limb with walking); unstable orthopedic, neurologic, or pulmonary conditions that limit physical function; unstable cardiac condition; uncontrolled hypertension; uncontrolled diabetes; acute systemic infection; active cancer treatment; or recent stroke (within 2 years).

Statistical power was estimated using variability estimates from our pilot data collection, where the change in physical activity (steps/day) was assessed in 42 participants (21 receiving intervention, 21 attention control) following TKA. The observed SD of percent change after 3 months of intervention for the pilot sample was 42%, with an effect size of  $d=0.64$ . This effect size equates to a detectable difference of 1,611 steps per day between groups. Based on this expected group difference, a 2-sample, 2-sided t-test at the 5% level with 80 patients (40 per group) would have 80.7% power to detect a group difference. We will enroll 100 participants (50 per group) to allow for a ~20% loss to follow-up. Previous clinical trials in our laboratory, for patients with TKA, have resulted in dropout rates of 4.9% and 6.5% at 3 months post-op and 8.2% and 15.2% at 12 months. Therefore, we are conservatively estimating a dropout rate of 20% at 9 months.

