***Exploratory Analysis (Exploratory Aim):*** The exploratory analysis will delineate the mechanisms underlying responsiveness to the PAB intervention by using multiple linear regression to identify key predictors of average daily step count from PREOP to POST2 in the PAB group. We will use the approach of fitting all possible models to identify the most parsimonious model predictive of the primary outcome of changes in steps per day across the intervention period. Candidate predictor variables will be those with theoretical evidence of predicting physical activity, including: PREOP steps per day, demographics (age, sex, education level), anthropometrics (height, weight, BMI), and comorbidities (Functional Comorbidity Assessment). In addition, we will focus specifically on physical activity-related psychosocial factors (depression, exercise self-efficacy, exercise readiness to change, social support, and fear of falling). The set of candidate predictor variables will be assessed for collinearity (and any collinearity reduced to the extent possible) before beginning model selection procedures. With  $k$  predictor variables, there are  $2^k$  possible regression models. Each of the  $2^k$  models will be fit and both 1) the adjusted  $R^2$  and 2) Mallows'  $C_p$  statistic will be generated for each model. A plot of Mallows'  $C_p$  vs  $p+1$  (where  $p$  = the number of model parameters) will be used to identify parsimonious candidate models according to Hocking's criterion. The best candidate models will be compared using their statistical properties as well as subject knowledge expertise and practical considerations (e.g. an objective variable may be preferred over a subjective variable). A final model will be selected from the candidate models. We hypothesize that baseline average steps per day at PREOP and all included psychosocial factors will be significant determinants of intervention responsiveness. The results of this exploratory aim will provide evidence for clinicians in determining the prognosis of patients in terms of likely physical activity improvement from the PAB intervention. We hypothesize that the PAB intervention will effectively increase physical activity, as measured in average steps per day. Whether that hypothesis is proven or not, the exploratory aim will add to the current body of rehabilitation knowledge by identifying key predictors of future activity based on baseline variables.

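### The exploratory aim expects every included psychosocial factor to be significant, but all-subsets selection in about 40–50 PAB participants cannot usefully test that

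*Combined protocol and SAP*

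**What the plan says.** Section F restricts the predictor analysis to one arm: it is "to identify key predictors of average daily step count from PREOP to POST2 in the PAB group". The method is "fitting all possible models to identify the most parsimonious model predictive of the primary outcome", using adjusted R², Mallows' Cp and Hocking's criterion. Collinearity is to be reduced first. The final choice among good models also draws on subject knowledge and practical considerations, and may favour an objective measure over a subjective one.

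The candidates are "PREOP steps per day, demographics (age, sex, education level), anthropometrics (height, weight, BMI), and comorbidities (Functional Comorbidity Assessment") plus five psychosocial factors: depression, exercise self-efficacy, readiness to change, social support and fear of falling. Section F then states the expectation: "We hypothesize that baseline average steps per day at PREOP and all included psychosocial factors will be significant determinants of intervention responsiveness".

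Hypothesis 3 in section I is worded differently. It expects that "physical activity-related psychosocial factors (self-efficacy, stage of change, social support, fear of falling) will be significant determinants of intervention responsiveness". It names four factors, omits depression, and does not say that all must be significant.

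No significance level, effect size, power or decision rule is given for this aim. The SAP describes no predictor regression; it says only that exploratory analyses followed the primary-outcome methods.

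**The concern.** Section F makes a claim about several terms jointly, and the sample was not sized for it. The sentence can be read in two ways. Either all the psychosocial candidates must be significant, or only those that survive into the final model. The first asks for six significant terms (PREOP steps and five factors) from one arm. The second judges terms by p-values computed on the data that selected them.

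The section means the results to inform clinicians' prognosis of activity gain. Sections E and G look ahead to using the predictors to dose and personalise the intervention in later work. A real factor left out of the selected model could be taken as unimportant, and a chance factor kept in it could be taken as established.

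**Working it through.** **Sample size.** The only sizing is for the primary comparison: a "2-sample, 2-sided t-test at the 5% level with 80 patients (40 per group) would have 80.7% power to detect a group difference". With d = 0.64, the noncentrality is 0.64 × √(40/2) = 2.86 on 78 df, which gives 80.7%. The stated figure reproduces, but it says nothing about this aim. For the PAB arm, "We will enroll 100 participants (50 per group) to allow for a ~20% loss to follow-up" gives 50 × 0.80 = 40. Earlier trials "have resulted in dropout rates of 4.9% and 6.5% at 3 months post-op and 8.2% and 15.2% at 12 months"; the 3-month rates give 50 × 0.951 = 47.6 and 50 × 0.935 = 46.8. So n is about 40–50.

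**Candidates.** Eight plus five is 13. If the collinearity step drops height and weight and keeps BMI (an assumption), 11 remain. Each factor is counted as one term.

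**Why joint significance is demanding.** If each test had 80% power and the tests were independent, all five would be significant with probability 0.8⁵ = 0.33, and all six with 0.8⁶ = 0.26. For a 50% chance that all six succeed, each needs power 0.5^(1/6) = 0.89.

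**Reading 1: all must be significant.** I simulated 11 candidates, of which six are true predictors with equal partial correlation r. The psychosocial factors correlate at 0 or 0.3. There were 400 runs per setting (Monte Carlo SE at most 2.5 points), all 2¹¹ subsets were fitted, and the minimum-Cp model was chosen. Success means that all six terms are selected with p < 0.05. The comparison is the full 11-term model without selection. Ranges run over the two correlations.

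| Partial r | n=40, selected | n=40, unselected | n=50, selected | n=50, unselected |
|---|---|---|---|---|
| 0.2 | 0% | 0% | 0% | 0% |
| 0.3 | about 1% | 0–0.5% | 2–3% | 1–1.5% |
| 0.4 | 10–13% | 5–7% | 22–30% | 14–19% |
| 0.5 | 45–52% | 31–40% | 70–71% | 60–62% |
| 0.6 | 86–88% | 76–81% | 97–98% | 94% |

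For six uncorrelated predictors the true R² is 6q/(1 + 6q), with q = r²/(1 − r²). At r = 0.3, q = 0.099 and R² = 0.37. At r = 0.5, q = 0.333 and R² = 2/3 = 0.67. At r = 0.6, q = 0.5625 and R² = 3.375/4.375 = 0.77.

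A second set-up used 12 candidates, slopes of 0.2–0.4 per predictor SD with residual SD 1, and the smallest model with Cp at or below its number of coefficients (250 runs per setting). All five psychosocial factors were kept with p < 0.05 in 0–9% of runs at n=40 and 0–20% at n=50; repeat runs gave 0–12% and 0–19%. On average about 1.5–3.9 of the five were kept.

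**Reading 2: only the kept factors count.** In the second set-up I gave PREOP steps a slope of 0.4 and the psychosocial factors none (400 runs per setting). At least one psychosocial factor was kept, and all those kept had p < 0.05, in 19–24% of runs. Also requiring PREOP steps to be significant would lower this rate. Given that any factor was kept, all the kept ones were significant in 60–63% of these null runs, against 63–83% when all five truly matter. The criterion barely separates the two cases.

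**The alternative.** A 5-df F-test of the psychosocial block in the unselected model rejected in 3–7% of the null runs. With all five real and R² of 0.32–0.66, its power was 70–99.6% at n=40 and 89–100% at n=50. With slope 0.2 and uncorrelated factors (R² 0.19) it was 38% and 56%.

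**The case against.** A reader might infer that parsimony causes the failure. The table does not support that: the unselected model confirms all six terms no more often than the selected one. The burden comes from several simultaneous tests in a small arm. What remains against selection is that a dropped factor gets no test and that p-values for kept factors are optimistic.

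A reader might also infer that the hypothesis would be rejected nearly always, and that the trial would report psychosocial factors as irrelevant. The documents set no accept-or-reject rule, label the aim exploratory, and nowhere say that an omitted factor will be reported as having no role. Some psychosocial factors would usually be kept. With strong effects the joint claim would often be confirmed.

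The simulations are also mechanical, whereas the plan adds judgement and a collinearity step. That is fair, and the percentages are only indicative. Judgement after seeing the fits does not repair the p-values, however, and a preference for objective measures would tend to work against questionnaire scales.

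Finally, a block test asks a different question: whether any factor matters. With only one of five factors real (slope 0.5, correlation 0.3) it was significant in 79% of runs at n=40 and 90% at n=50. This objection stands and limits how the test may be worded. The power of the block test and the chance that all five are significant are not like for like.

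**Conclusion.** The point holds in a limited form. Section F states an expectation that its own procedure cannot usefully test. If all factors must be significant, confirmation is about 0–20% at slopes of 0.2–0.4, and at most about 3% at partial r of 0.2–0.3. It becomes likely only at about 0.5–0.6 or more for every factor, which needs a true R² of roughly 0.67–0.77 even when the factors are uncorrelated. If only kept factors count, the psychosocial claim is met in about 20–25% of runs when none of them matters.

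All these figures rest on assumed effect sizes, correlations and selection rules, because the documents give none for this aim. The primary comparison is unaffected. This is a cheap improvement to an exploratory analysis, and the documents do not show that a false negative conclusion will be published.

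**What to change.** 1. Reconcile the factor lists in section I and section F. Say whether depression belongs, and what the expectation about the included factors means.
2. Prespecify one model without selection: PREOP steps, demographics, anthropometrics, comorbidity and the psychosocial block, after a collinearity step that does not look at the outcome.
3. Report each coefficient with its 95% CI, and one joint F-test of the block (5 df, or 4 df without depression). Word it as a test of whether the psychosocial factors as a set add to prediction, not as evidence that every factor matters.
4. Keep the all-subsets search as description, and state that omission from the selected model is not evidence of no association.
5. Put this in the SAP, which does not describe the regression.

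The cost is a few sentences, and one model fitted with and without the block, on data already collected. The downsides are that the block test does not say which factor matters, and that the individual intervals will be wide: with 11 predictors and n = 40, only 40 − 11 − 1 = 28 residual df remain.

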#### **G. Summarize Knowledge to be Gained:**

This study is an essential step for providing foundational evidence to support the effectiveness of a telerehabilitation approach aimed to increase physical activity in patients with TKA. The ultimate goal of this research line is to 1) develop and refine methods for implementing findings of the current study into clinical rehabilitation practice and 2) effectively disseminate these intervention methods to clinical institutions, both nationally and internationally. We will work with the Denver GRECC to develop strategies for operational partnerships both locally and nationally through Home Based Primary Care programs and through connections with other GRECC Associate Directors for Clinical Programs. In addition, [name] has developed strong working collaborations with the Center for Research in Implementation Science and Prevention (CRISP) at the University of Colorado Denver to facilitate additional strategies for rapid transition to implementation strategies immediately upon conclusion of the proposed investigation.

*Personalized Rehabilitation to Optimize Utilization.* Current rehabilitation guidelines after TKA are generalized based on population expectations. However, there is high individual variability within the population of Veterans undergoing TKA and thus, we expect variable responses to rehabilitation. By identifying the key predictors of responsiveness to intervention, we expect the results of our study to lead to methods for individually tailored approaches to personalize rehabilitation practices, which will optimize Veteran outcomes and lower overall costs.

*Application of Findings to Other VA Populations.* Future investigations could apply the proposed PAB rehabilitation to other populations with chronic physical activity deficits. We expect our findings to be generalizable to a variety of populations of Veterans who are routinely seen for orthopedic surgeries and other medical conditions. We chose to initially focus on TKA because of the high utilization of TKA, the great need to improve physical activity in these Veterans, and the ability to capitalize on the “teachable moment” of elective TKA surgery.

## Statistical Analysis Plan

An intention-to-treat approach was used for the primary data analysis. The two treatment arms were compared by demographics and baseline clinical characteristics using standardized mean difference and confidence intervals. Observed means of the primary and secondary outcomes were calculated. To assess group differences in the primary outcome (average daily step count), a linear mixed model (LMM) was used. The LMM accounted for the within-subject correlation associated with repeated measures through the inclusion of a random intercept for subject. Decade of participant age was included in the LMM as a continuous fixed effect. The model also included as fixed effects time and an interaction between intervention arm and time. Between-group difference at baseline was set at zero, so estimated baseline scores were equal between groups.

The primary analysis was conducted using the first 3 time points (pre-surgery, 8 weeks post-surgery, 14 weeks post-surgery), and the test of intervention effect on daily step count was tested using a Likelihood Ratio Test (LRT). P-values for the effect of intervention were derived from a LRT comparing the model with interaction of intervention arm and time versus the reduced model without the interaction. Contrasts were used to estimate group means and confidence intervals.

Secondary and exploratory analyses used the same methods as the primary outcome (pre-surgery, 8 weeks post-surgery, 14 weeks post-surgery, and 38 weeks post-surgery), and week 38). A secondary LMM analysis with the four time points was also conducted to test for group difference in daily step count at Week 38. All analyses were performed using R statistical software version 4.3.0.

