#### *Physical Activity Description for Patients with TKA after Progressive Rehabilitation*

The idea for the PAB intervention was supported by our initial sub-analysis of participants from a recently completed randomized controlled trial (NIH R01-D065900). The intervention of the parent trial involved progressive resistance strengthening exercise to improve functional outcomes. The progressive group was compared to a group of patients receiving traditional rehabilitation after TKA. We hypothesized that the progressive strengthening group would demonstrate superior outcomes in terms of strength, functional performance, and mobility when compared to traditional rehabilitation. Within that study, we performed a sub-analysis to examine physical activity before and after rehabilitation in a subset of participants from both groups using accelerometry (ActiGraph GT3X, ActiGraph Corporation, Pensacola, Florida). We measured physical activity in terms of average steps per day over a one-week period at five time points: before (2 weeks) and after (1, 3, 6, and 12 months) surgery.

This preliminary study showed no significant change in steps/day for the entire cohort, the traditional group, or the progressive strengthening group (Table 2). In other words, mode of rehabilitation

Table 1. Daily Step Count Before and After Total Knee Arthroplasty

Time Point	Traditional Control Group	Progressive Strengthening Group	Total
Pre-Operative	5047 ± 2105	6071 ± 2341	5623 ± 2230
Month 1 Post-Operative	3201 ± 2269 ; $p = 0.146$	3994 ± 2518; $p = 0.257$	3598 ± 2323; $p = 0.046$
Month 3 Post-Operative	3625 ± 1170 ; $p = 0.963$	5942 ± 3518; $p = 0.295$	5512 ± 2633; $p = 0.563$
Month 6 Post-Operative	5704 ± 2966 ; $p = 0.004$	6299 ± 2976; $p = 0.857$	6001 ± 2870; $p = 0.210$
Month 12 Post-Operative	5895 ± 3150 ; $p = 0.075$	6450 ± 3923; $p = 0.381$	6151 ± 3385; $p = 0.092$

Note: Data are presented as mean ± SD; p-values are comparisons to Pre-Operative visit.

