#### IV. Research Methods

##### A. Outcome Measure(s):

**Descriptive Variables.** Baseline descriptive measures will include demographics (age, sex, education level), anthropometrics (height, weight, BMI), comorbidities (Functional Comorbidity Assessment), depression (Geriatric Depression Scale SF), cognition (Folstein Mini-Mental State Exam^34), exercise self-efficacy (Self-Efficacy for Exercise Scale), exercise readiness to change (Exercise Stages of Change), social support (Multidimensional Scale of Perceived Social Support), and fear of falling (Falls Efficacy Scale-International). These descriptive variables will be used as candidate predictor variables for change in accelerometer-based physical activity.

**Accelerometer-based Activity Monitoring.** The primary outcome for this study will be accelerometer-based physical activity (average daily step count) objectively monitored for all participants over a 7-day period, at all four test points. Participants will wear an activPAL micro accelerometer-based sensor (PAL Technologies, Glasgow, UK) to measure physical activity. The activPAL sensor is a small (23.5x43x5 mm) and lightweight (10 g) device that uses accelerometer-derived information about thigh position to estimate daily step count and time spent in different body positions (e.g. sitting/lying, standing and stepping) with high level of accuracy (99-100%). The sensor will be placed in a small nitrile sleeve and wrapped with a non-allergenic water-proof dressing on the midline of the thigh, approximately 1/3 distance between the hip and knee. Because the activPAL is wrapped in a waterproof dressing, participants will be instructed to wear it at all times (including sleep) except when swimming. The event data file from the activPAL software will be used to determine time spent sitting/lying, standing, and

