#### *Data Collection and Outcomes*

Preoperative testing will occur 2 weeks prior to TKA (PREOP). Postoperative testing will occur midway through the PAB intervention (POST1), at the end of PAB intervention (POST2), and 24 weeks after PAB intervention (approximately 9-months after TKA) (POST3). The POST1 test will assess early between-group responses to intervention, while the POST2 test will assess group differences at intervention end (Primary End Point). The POST3 test is critical, as a key component to assessing success of behavior change is the long-term persistence of behavior change. Each test session will include the standardized procedures described in the next sections. Importantly, all test sessions occur at participant homes, to eliminate time and travel burdens for the participants and minimize barriers for rural participants. The 30-Second Chair Stand Test and Timed-up-and Go may be conducted remotely via video call and surveys may be conducted via phone/video call or through REDCap. Semi-structured interviews will occur following randomization, and again following the POST2 assessment period. Up to 20 participants will be randomly selected from the PAB group to have at least 10 participants participate in semi-structured interviews at both time points. An interview guide will be used with questions regarding the PAB program, perceptions of barriers and facilitators to physical activity, and perceptions of participation in everyday life. Depending on participant preference the interview can occur in-person, over the phone, or via an audio-visual application. All interviews will be audiorecorded and transcribed verbatim by a research team member or an approved transcription service.

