## **F. Data Analysis Plan:**

The primary outcome for this study is average number of steps taken per day, as measured by accelerometer-based wearable sensors (activPAL) over a 7-day period at the end of the intervention. This time point is chosen for clinical relevance to establish efficacy of the intervention. Sustainability will be tested as a secondary outcome, by assessing steps taken per day six months after conclusion of the intervention period. Other secondary outcomes include time spent in standing/walking activities and physical function measures. Preliminary descriptive and graphical analyses (including boxplots, scatterplots, profile plots of change over time) will be used for data cleaning, data visualization, and assessing statistical assumptions.

***Primary Analysis (Aim 1):*** The primary analysis will be an intent-to-treat comparison of the differences between the study groups (PAB and CTL) in the change average daily step count from PREOP to POST2 (primary endpoint). Statistical inference will be based on the estimated coefficient for the group variable using an analysis of covariance (ANCOVA) model with change in average daily step count from PREOP to POST2 as the response variable. Additional covariates include the stratification variables (PREOP physical activity and age) to improve the precision of the estimate. The conclusion about group differences will be made based on this single statistical test to control the type I error rate at 0.05. A similar between-group analysis will be performed on the change in daily step count from PREOP to POST3 (6-month effect post-intervention). A sensitivity analysis will be done to evaluate whether conclusions would differ when other covariates are added to the model (e.g., demographics, anthropometrics, comorbidities, psychosocial factors).

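### The SAP states only a random intercept; if step-count spread grows after surgery, as the documents' small earlier samples suggest, the week-38 intervals would be too narrow, while the primary P-value is little affected

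*Combined protocol and SAP*

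**What the plan says.** The Statistical Analysis Plan fits a linear mixed model to daily step count: "The LMM accounted for the within-subject correlation associated with repeated measures through the inclusion of a random intercept for subject". The fixed effects are time, arm-by-time and decade of age, and the arms are constrained to be equal at baseline. It mentions no visit-specific residual variance, unstructured covariance or robust standard error.

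The same covariance model feeds every inference. For tests: "P-values for the effect of intervention were derived from a LRT". For estimates: "Contrasts were used to estimate group means and confidence intervals". The primary model uses three visits (pre-surgery, weeks 8 and 14). For later follow-up: "A secondary LMM analysis with the four time points was also conducted to test for group difference in daily step count at Week 38". Secondary outcomes follow the same methods.

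The protocol (section IV.F) planned something different: an ANCOVA on the change from PREOP to POST2, a single test "to control the type I error rate at 0.05", with a similar analysis of change to POST3 and the same approach for the secondary outcomes.

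**The concern.** A random intercept with a single residual variance averages the variance over visits. If the true spread is larger at late visits than before surgery, the averaged variance understates the uncertainty of late contrasts and their intervals are too narrow.

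The documents give reason to suspect this. In Table 1 (section III) the SD rises from the pre-operative visit to month 12 in every column: Total 2230 to 3385, Traditional 2105 to 3150, Progressive 2341 to 3923. In the PAB pilot it rises in both arms: 3003 to 3677 and 1544 to 2388. Nothing in the documents supports a constant variance.

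Week 38 is most exposed because it lies furthest from baseline. It is POST3, 24 weeks after the intervention ends, and the protocol says of it: "The POST3 test is critical". The claim that the effect persists rests on that interval.

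**Working it through.** **Sample size used.** Section IV.B gives 80.7% power for 40 per group at d = 0.64, two-sided 5%. The noncentral t gives 80.70%, so the figure reproduces. I use 40 per arm with complete data.

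**How much Table 1 can carry.** It prints no group sizes, but column means and SDs together with the Total mean and SD recover them. Searching 2 to 40 per column gives one solution per row (Traditional + Progressive): pre-operative 7+9 (implied Total SD 2229.5, printed 2230), month 1 6+6, month 6 7+7, month 12 7+6 (3384.8, printed 3385). Each row is therefore about 12 to 16 people.

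- Variance-ratio tests, month 12 against pre-operative: Total (3385/2230)² = 2.30, p = 0.13; Traditional p = 0.35; Progressive p = 0.19.
- A paired (Pitman-Morgan) test on Total: p = 0.15, 0.10 and 0.04 at assumed correlations 0.4, 0.6 and 0.8.

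**Month 3 is left out.** No sizes up to 40 per column reproduce that row. Its means imply a Progressive share of (5512 − 3625)/(5942 − 3625) = 0.814 and hence a combined SD near 3338, against 2633 printed. It also gives p = 0.963 for a fall from 5047 to 3625 in the Traditional group.

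**SDs at the trial's visits.** Linear interpolation between months 1, 6 and 12 (weeks 4.33, 26 and 52). Total at week 38: 2870 + (12/26) × (3385 − 2870) = 3108.

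**Formulas.** Let v be the average variance over visits, c the average covariance, b = c/v, n = 40, and ρ the common true correlation (not in the documents; 0.4 to 0.8 assumed). With a zero baseline difference, the arm contrast at visit j is the difference at j minus b times the difference at baseline. Then:

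- variance the model reports: (2/n) × v × (1 − b²)
- true variance: (2/n) × (σj² − 2bρσjσ0 + b²σ0²)
- non-coverage: 2 × [1 − Φ(1.96 × model SE / true SE)]
- LRT size: the weighted chi-square whose weights are the eigenvalues of (model covariance)⁻¹ × (true covariance) of the arm-by-time contrasts

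**Worked case: Total, ρ = 0.6, week 38, four visits.** v = (2230² + 2416² + 2567² + 3108²)/4, about 6.76 million; b = 0.587. Model SE = √(0.05 × 6.76 million × 0.655) = 471. True SE = 570. The ratio is 0.826, so non-coverage is 10.5%. At week 14 (three visits) the SEs are 432 and 462, giving 6.7%.

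| Column | SD at PREOP, wk 8, 14, 38 | Week 14 misses (3 visits) | Week 38 misses (4 visits) | 3-visit LRT size |
|---|---|---|---|---|
| Total | 2230, 2416, 2567, 3108 | 6.6–6.8% | 10.2–11.4% | 6.1–6.2% |
| Traditional | 2105, 2387, 2580, 3051 | 7.3–7.6% | 10.3–11.7% | 6.6–6.7% |
| Progressive | 2341, 2596, 2722, 3413 | 6.6–6.8% | 11.0–12.5% | 6.3% |

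Ranges run over ρ = 0.4 to 0.8. With equal SDs and one common correlation every entry returns to 5%.

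**The alternative.** With complete data the unstructured ML likelihood ratio test has an exact size from the F distribution: 5.8% for three visits and 6.1% for four, whatever the SDs. For the primary test it is therefore better by only 0.3 (6.1 − 5.8) to 0.9 (6.7 − 5.8) of a point. Simulated unstructured contrasts on 77 degrees of freedom missed 4.7% to 5.2% of the time at both weeks.

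**The case against.** Five things can be said for the plan.

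1. **The SAP is a short summary.** A random intercept does not exclude visit-specific residual variances, so they may have been fitted. This stands: the defect is that the structure is not stated, not that a wrong one is proven.

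2. **The evidence is thin.** Table 1 is a sub-analysis of an earlier trial "in a subset of participants from both groups using accelerometry (ActiGraph GT3X"), whereas here "Participants will wear an activPAL micro accelerometer-based sensor". The pilot had 14 per group and began as outpatient therapy was ending, so its first measurement is not pre-surgical. This stands too. A reader might infer that the documents show the variance to be unequal. They do not: none of the variance-ratio tests is significant, and the paired test falls below 0.05 only if the correlation is as high as 0.8.

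3. **The primary P-value hardly moves.** A reader might infer that the SAP's test loses control of the 5% error rate. A size of 6.1% to 6.7%, against 5.8% for the unstructured test, does not support that.

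4. **The week-14 error could look much larger, or reversed.** If month 3 of Table 1 is used, week-14 non-coverage runs from 0.9% (Traditional) to about 11% (Progressive) on interpolated SDs. That spread comes from a row that does not reconcile with itself. Without it the three columns agree on slightly narrow intervals.

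5. **The protocol already holds a robust check.** Its change-score ANCOVA needs no equality of variance across visits. This stands, and it belongs in the remedy.

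None of these removes the week-38 result: without month 3 the interval is too narrow in all three columns.

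**Conclusion.** The concern holds as a conditional point about interval precision, chiefly at POST3. If the spread grows as in the usable rows of Table 1, nominal 95% intervals for the arm difference would miss about 10% to 12.5% of the time at week 38 and 6.6% to 7.6% at week 14. The primary test would sit about one to two points above 5%.

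This rests on 40 per arm, complete data, the same SDs in both arms, one common correlation of 0.4 to 0.8 that the documents do not give, interpolated SDs from about 12 to 16 people measured with another sensor, and the ordinary reading of the random intercept. If instead correlation falls with time between visits, week-38 coverage drops to about 0.87 to 0.91 even with equal SDs, so an unstructured fit answers both possibilities.

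A reader might go further and conclude that the primary model is invalid and must be replaced. The documents do not support that: the effect on the primary test is small, and the SAP is written in the past tense, so the analysis appears to have been run. Changing the primary model now would be a choice made after results exist.

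**What to change.** State the residual covariance structure actually used. Then add two sensitivity analyses at weeks 14 and 38, for step count and the secondary outcomes:

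- the same fixed effects and zero baseline difference with an unstructured covariance across visits (6 parameters for three visits, 10 for four), fitted by REML, with Satterthwaite or Kenward-Roger degrees of freedom for contrasts and intervals;
- the change-score ANCOVA prespecified in section IV.F of the protocol.

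Keep the existing model as primary. If the week-38 interval differs materially, base the conclusion on persistence on the unstructured interval, and say so.

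The cost is SAP wording, a model re-run and a few more covariance parameters. Intervals may widen. If the SDs are in fact equal, the contrast standard error grows by only about 0.7% at 40 per arm.
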